#### 10.7 **Study Follow Up**

Study-related follow-up visits occur at the investigational site at Week 2, Week 4, Week 6, and Week 12. The study's schedule of assessments is shown in Table 3.

# 10.7.1 Visit 4/2 Weeks Post-op (14 ±3 Days), Visit 5/4 Weeks Post-op (28 ±5 Days), and Visit 6/6 Weeks *Post-op (42 ±5 Days)*

Subjects will be evaluated and data collected per the schedule of events. Any changes in concomitant medications/concurrent procedures will be documented. Any anticipated observations, adverse events, adverse device effects and/or SAE/UADE/USADE will be assessed and documented. Photographs may be taken of the treatment area.

The Subject will complete a WOMAC questionnaire, NRS for Pain when standing from a seated position, PROMIS questionnaire, and SF-36 questionnaire. Subjects will be asked to assess their treatment assignment (the blind).

Subjects will answer Satisfaction questions at Visit 6.

The subject will complete the Physical Performance Measures in the following order under supervision of the investigator or designee:

- Active Range of Motion
- 40 Meter Walk Test
- 30 Second Chair Test

Detailed instructions for the conduct of these performance measures are included in the Study Operations Manual. Assistive/ambulatory device usage and work status will also be assessed.

Utilization of healthcare services post-discharge, or since the previous follow-up visit, will be assessed. Subjects will be asked to report any Secondary Surgical Interventions, Emergency/Urgent care visits, Unscheduled physician office visits, and other healthcare services used since their last study visit. Investigators will also record any additional or unscheduled services performed at follow-up visits (examples include knee aspiration, unscheduled x-ray, other unscheduled diagnostic procedures, etc.).

Subjects will be asked to bring all prescription opioid bottles to all study follow-up visits. A pill count will be completed by the study coordinator, or designee, and opioid medication will be redispensed to subjects.

## 10.7.2 Visit 7/12 Weeks Post-op (84 $\pm$ 7 days)

Subjects will be evaluated and data collected per the schedule of events. Any changes in concomitant medications/concurrent procedures will be documented. Any anticipated observations, adverse events, adverse device effects and/or SAE/UADE/USADE will be assessed and documented. Photographs may be taken of the treatment area.

The Subject will complete a WOMAC questionnaire, NRS for Pain when standing from a seated position, PROMIS questionnaire, and SF-36 questionnaire. Subjects will answer Satisfaction questions. Subjects will be asked to assess their treatment assignment (the blind).

The subject will complete the Physical Performance Measures in the following order under supervision of the investigator or designee:

- Active Range of Motion
- 40 Meter Walk Test
- 30 Second Chair Test

Detailed instructions for the conduct of these performance measures are included in the *Study Operations Manual*. Assistive/ambulatory device usage and work status will be assessed. The total number of outpatient Physical Therapy visits conducted between hospital discharge and 12 Weeks post-op will also be obtained.

Utilization of healthcare services since the last follow-up visit will be assessed. Subjects will be asked to report any Secondary Surgical Interventions, Emergency/Urgent care visits, Unscheduled physician office visits, and other healthcare services used since their last study visit. Investigators will also record any additional or unscheduled services performed at follow-up visits (examples include knee aspiration, unscheduled x-ray, other unscheduled diagnostic procedures, etc.).

Subjects will be asked to bring all prescription opioid bottles to all study follow-up visits. A pill count will be completed by the study coordinator, or designee, and opioid medication will be redispensed to subjects.

At the completion of this visit, the Subject will be exited from the study unless the Subject has any ongoing device-related or iovera° treatment-related adverse events as described in section 10.8.

**Table 3. Schedule of Assessments** 

Table 5. Schedule of Assessments							
	Visit 1 / Screening	Visit 2 / iovera° Treatment	Visit 3 / DAY OF TKA (Day 0)	Visit 4 / 2 Weeks Post-op	Visit 5 / 4 Weeks Post-op	Visit 6 / 6 Weeks Post-op	Visit 7 / 12 Weeks Post-op
Assessment Informed Consent	X						
	X	v					
Eligibility	X	X					
Medical history Concomitant medication	X	A					
assessment	X	X	X	X	X	X	X
Prior/Concurrent Therapy	X	X		X	X	X	X
Randomization*		X					
Study Treatment		X X X X					
Physical Exam		X					
Vital signs	X	X					
Knee Circumference		X					
PROMIS Questionnaire	X			X	X	X	X
WOMAC Questionnaire	X			X	X	X	X
SF-36	X			X	X	X	X
NRS for Pain	X			X	X	X	X
Work Status Questions	X			X	X	X	X
Subject Satisfaction Questions						X	X
Assessment of Blind		X		X	X	X	X
Physical Performance Measures	X			X	X	X	X
Pain Medication Accountability				X	X	X	X
AE/SAE Assessment		X	X	X	X	X	X
Photographs (if applicable)		X		X	X	X	X

\* Randomization occurs after the subject has met eligibility criteria and prior to or at Visit 2

Follow-up visits generally consist of the following:

- The Investigator or designee assesses the occurrence of health status changes and adverse events since last study visit;
- The Investigator or designee determines whether any changes in daily medications have occurred;
- The Investigator or designee performs drug accountability (pill counts) of postoperative outpatient opioid medication and re-dispenses unused opioid medications to subjects after use. The Investigator or designee records other over-the-counter concurrent pain medication use and pain relief therapies used per subject report;
- The Subject completes a WOMAC questionnaire, an SF-36 questionnaire, PROMIS questionnaire, Work Status Questions, Satisfaction questions (Visits 6 and 7 only),

self-assessment of the blind, and reports NRS for Pain when standing from a seated position;

• The Investigator or designee performs Physical Performance Measures (Range of Motion, 30 Second Chair Test and 40 Meter Walk Test).

#### 10.8 **Photographs**

Photographs may be taken of the treatment area at the treatment visit and at the follow-up visits. Photographs will be labeled appropriately, stored electronically (e.g., JPEG, PNG or other relevant format) and sent to the Sponsor according to Sponsor instructions.

#### 10.9 **Study Exit**

When the final study visit is complete, the Subject's participation in the study is complete and the Investigator, or designee, will complete the study exit eCRF.

If a Subject is experiencing an unresolved device or iovera° treatment related adverse events at the final study visit, the Subject will be followed by the Investigator until resolution occurs

# **10.10** Subject Discontinuation

A Subject may be withdrawn from the study prior to completion for any of the following reasons:

- Voluntary withdrawal of consent
- Adverse event preventing continued study participation
- Investigator believes risk of further subject participation outweighs benefit
- Medical need for prohibited medications or treatment
- Persistent non-compliance or lost to follow-up (A Subject is considered lost to followup after the site makes 3 attempts to contact the via email or phone call and a certified letter is sent to the Subject.)

The Investigator/Coordinator will complete a study exit form in the eCRF for any subject who prematurely discontinues from the study. If discontinuation was the result of an AE, the AE will also be recorded in the eCRF

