#### 10.5 iovera° Treatment/Visit 2 (-07 - 0 Days prior to TKA)

Medical history will be reviewed as well as concomitant medications and procedures. Blood pressure and heart rate will be assessed. The Investigator, or designee, will reconfirm all eligibility criteria are met.

The iovera° device will be prepared by the trained Investigator (or Sponsor designee) according to the *User Guide*. If at any time the device does not perform as expected the Investigator (or designee) will follow procedures as outlined in the *User Guide*.

Prior to the initiation of the iovera° treatment, the Investigator, or designee, will mark the treatment lines on the knee to be treated as shown in Figure 2 located in section 9.2. After marking the treatment lines, the study coordinator or designee will measure the knee circumference at the treatment lines per guidance in the *Study Operations Manual*.

Then the skin along the treatment lines will be cleansed with alcohol. Lidocaine, no epinephrine, will be injected along the treatment lines superficially in order to achieve cutaneous anesthesia and to the bottom of the subcutaneous layer, atop the fascia, to temporarily block conduction of the infrapatellar branch of the saphenous nerve and the anterior femoral cutaneous nerve.

Once localized anesthesia of the treatment lines and the nerves is achieved, the Investigator, or designee, will complete the iovera° treatment along the treatment lines. Regardless of the length of treatment lines (width of patella or from lower pole of the patella down to tibial tubercle), adjacent insertions are placed along the treatment lines until the entire line has been treated so all Subjects receive the same treatment. Treatment is not to be modified or influenced by any Subject response to changes in knee pain. Representatives of myoscience, Inc. may be present during the treatment. Photos of the treatment area may be taken.

Upon completion of treatment, the treatment areas will be cleansed and the skin will be left undressed. The Investigator or designee will assess the treatment areas for adverse events. Subjects will be asked to assess their treatment assignment (the blind).

The Subject will be instructed to report any adverse events to the Investigator between and at the follow-up visits. Photographs of the treatment area may be obtained post-treatment.

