#### 11.5 **Handling of Dropouts or Missing Data**

All endpoints will be analyzed "as-is" without any special data imputation methods used to replace missing data. Consequently, subjects missing results for a specific analysis will be excluded from that analyses.

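### Section 10.10 permits withdrawal from the study, not just from treatment, for non-compliance or an undefined prohibited-treatment need, so primary opioid data that could still be collected may be lost

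*Protocol*

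**What the plan says.** Protocol section 10.10 opens: "A Subject may be withdrawn from the study prior to completion for any of the following reasons". The object is the study, not the treatment. Besides withdrawal of consent, the reasons are "Adverse event preventing continued study participation", "Investigator believes risk of further subject participation outweighs benefit", "Medical need for prohibited medications or treatment" and "Persistent non-compliance or lost to follow-up". For what follows, the section says that the site "will complete a study exit form in the eCRF for any subject who prematurely discontinues from the study", and that an adverse event which caused the discontinuation is also recorded. It does not provide for further pill counts or medication records.

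Section 10.5 places the treatment in a single session during the week before surgery or on the day itself. From then on the study's contribution is observation at Weeks 2, 4, 6 and 12 (section 10.7).

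The primary endpoint (section 11.2.1) is opioid use between discharge and Week 6, expressed per day. It is analysed in the Per-Protocol Cohort (11.3.4), whose definition (11.3.3) requires a completed Week 6 visit and no major deviation. Under section 11.5 nothing is imputed and "subjects missing results for a specific analysis will be excluded from that analyses". Section 11.9, by contrast, says that every randomized patient enters every analysis.

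**The concern.** Once the session at Visit 2 is over, no study treatment remains to be stopped. Ending participation then protects the subject from little, and the trial gives up outcome data that scheduled visits would have supplied.

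Two of the reasons need closer attention. The prohibited-treatment reason has no content: the word occurs nowhere else in the protocol and no list is given, so centers may apply it differently. Persistent non-compliance is a reason to work harder on data collection, not a reason to stop it while the subject can still be reached.

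Both arise after randomization and could plausibly be related to recovery, and so to opioid use. If they remove different kinds or numbers of subjects from the two arms, the t-test no longer compares randomized groups. A later switch to an all-randomized analysis would not bring back data that were never collected.

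The same loss affects the Week 6 WOMAC Pain comparison (11.3.5, 11.5). It also affects safety: section 12 records adverse events only to exit or early withdrawal, while section 11.1 sets the primary safety endpoint through twelve weeks.

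**Working it through.** **1. From withdrawal to loss of the primary outcome.**
- 10.10: the subject leaves the study and an exit form is completed.
- 10.7: later pill counts are tied to study visits, which no longer take place.
- 11.3.3 and 11.3.4: without a Week 6 visit the subject is outside the primary cohort, even if Week 2 or Week 4 counts exist.
- 11.5: nothing replaces the missing value.

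**2. Is any treatment prohibited?** Section 10.6 limits procedural anesthesia to spinal and requires a single-shot adductor canal block, but it records post-operative, over-the-counter and other pain treatments as data. Sections 10.7.1 and 10.7.2 collect further surgery, emergency visits and unscheduled procedures from subjects still in follow-up. None of these is called prohibited.

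**3. The plan's own figure.** Inputs from section 11.10: difference 7.14 mg/day, SD 13.1 mg/day, one-sided alpha 0.025, power 0.80. The exact two-sample t-test has power 0.794 at 53 per group and 0.801 at 54, so the stated 54 reproduces. The 10% allowance leaves 150 × 0.9 = 135 subjects, about 67 per group, with power about 0.88. Lost power is therefore not the issue; bias is.

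**4. Illustration of the shift in one arm.** Suppose a fraction f is lost, with mean k SDs above the arm mean. The full arm mean is the weighted average of lost and retained subjects, so the retained mean falls by

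f/(1 − f) × k × 13.1 mg/day.

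- f = 0.10, k = 1: 0.1111 × 13.1 = 1.46 mg/day; 1.46/7.14 = 20%.
- f = 0.05, k = 0.5: 0.0526 × 0.5 × 13.1 = 0.34 mg/day; 5%.
- f = 0.10, k = 1.5: 0.1111 × 1.5 × 13.1 = 2.18 mg/day; 31%.

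The values of k are assumptions. The 10% is the protocol's allowance for all early withdrawal and missing primary data, so placing all of it in one arm as selective loss is generous to the concern.

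**5. What matters is the difference between arms.** With k = 1, loss of 10% in one arm and 5% in the other shifts the difference by 1.46 − 0.69 = 0.77 mg/day, or 11% of 7.14. Loss of 10% in both arms at the same k shifts it by 1.46 − 1.46 = 0.

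**6. A worst case.** Assume normal daily use, 75 per arm, and that exactly the highest users are lost. With c the standard normal quantile at 1 − q, the retained mean falls by φ(c)/(1 − q) × 13.1.
- q = 0.05: 0.1086 × 13.1 = 1.42 mg/day.
- q = 0.10: 0.1950 × 13.1 = 2.55 mg/day.
- 10% lost in active, 5% in sham: the difference moves by −1.13 mg/day and the one-sided type I error rises from 0.025 to about 0.084.
- 5% lost in active, 10% in sham: the difference moves by +1.13 mg/day, the type I error falls to about 0.006, and a real effect is understated.

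**The case against.** The strongest reply is that section 10.10 permits and does not compel. A reader might infer that sites are told to stop collecting data on the hardest-recovering subjects. The text does not support that. It says a subject may be withdrawn, and the adverse event reason covers only events that already prevent participation. That the withdrawn would be the heavier opioid users is plausible, but the protocol nowhere says so.

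A reader might also infer that any subject given extra analgesia or a further procedure could be removed as needing prohibited treatment. Sections 10.6 and 10.7 point the other way, since they record both as ordinary study data. What remains is an undefined term, not a mechanism for removing such subjects.

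Three further points stand. Part of the exclusion comes from the Per-Protocol definition, because early pill counts may exist for a withdrawn subject; amending 10.10 alone would not bring those subjects into the primary analysis. Section 10.10 also applies between consent and treatment, when some of the reasons may have a purpose. And the investigator's risk-benefit reason protects subjects and should not be deleted.

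None of this answers the central gap: after treatment the protocol allows follow-up to end for two reasons that do not require it, and makes no provision for opioid data afterwards. A statistical analysis plan cannot supply data that sites did not collect.

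**Conclusion.** The point holds as a correctable weakness in follow-up. For treated subjects, section 10.10 allows avoidable loss of primary-outcome data through persistent non-compliance and an undefined prohibited-treatment reason. Sections 11.3.3, 11.3.4 and 11.5 then turn that loss into exclusion from the primary analysis. Section 11.9 contradicts those sections on who is included.

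The size cannot be derived from the protocol. About 1.5 mg/day (range 0.3 to 2.2) in one arm's mean is an illustration that rests on assumed values of f and k and on loss confined to that arm. It would be wrong to conclude that the treatment effect will be overstated. Loss mainly from sham would understate it, loss mainly from active would overstate it, and equal, similarly selective loss leaves the difference unbiased. The amendment is worth making because it is cheap and the lost data could not be recovered afterwards.

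**What to change.** Amend section 10.10 for treated subjects as follows.

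- Remove the prohibited-treatment reason and persistent non-compliance as grounds for ending follow-up, and record such events as data.
- State that subjects who have not withdrawn consent, been lost to follow-up or died continue pill counts, medication records, WOMAC and adverse event collection at the remaining scheduled visits, by phone or from records if they cannot attend.
- Keep the investigator's risk-benefit reason and the reason for adverse events preventing participation, but still collect opioid and adverse event data where the subject agrees.

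In section 11, state that incomplete follow-up after such events does not by itself exclude available opioid data, align 11.3.3 with that, and reconcile 11.9 with 11.3.4 and 11.5.

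This concerns data collection only and takes no view on which treatments subjects may receive. The cost is a short amendment, a matching change to the exit form, and a few more follow-up contacts that are already on the schedule.

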## **10.11 Study Termination**

The Sponsor may terminate the study as a whole or at individual study sites under the following circumstances:

- Suspicion of risk to subjects, including occurrence of high rate of known AEs or unexpectedly high rate of unexpected AEs
- Poor site compliance with the study protocol
- Inadequate site enrollment
- Obtaining new scientific knowledge that shows that the study is no longer valid or necessary
- Persistent non-compliance with IRB or regulatory requirements
- Persistent failure to comply with obligations arising from the clinical trial agreement

• Other business reasons (e.g., insolvencies or business entity liquidation)

The Sponsor will document reasons for study suspension and notify relevant site Investigators and governing IRBs. If suspension occurred because of a safety issue, all Investigators will be notified. When terminating the study, the Sponsor and Investigator will assure that adequate consideration is given to the protection of the subjects' interests.

# **10.12** Study-Related Assessments

# 10.12.1 Western Ontario and McMaster Osteoarthritis Index (WOMAC)

The WOMAC is a tri-dimensional, disease-specific, patient-reported outcome measure. It consists of 24 questions with 5 questions regarding pain, 2 questions regarding stiffness and 17 questions regarding function. A copy of the WOMAC is located in Attachment 1.

Completion of the WOMAC questionnaire will take approximately 15 minutes to complete. After completion by the Subject, the study coordinator or designee will enter into the eCRF.

# 10.12.2 Numeric Rating Scale for Pain (NRS for Pain)

The Numeric Rating Scale for Pain (NRS for Pain) is a measure of pain intensity. The investigator or designee conducts the 11-point scale verbally with the research subject in reference to the target knee. The investigator or designee will ask the following questions,

- "On a scale of 0 to 10, with 0 being no pain at all and 10 being the worst pain imaginable, how would you rate your pain RIGHT NOW when standing from a seated position."
- "On a scale of 0 to 10, with 0 being no pain at all and 10 being the worst pain imaginable, how would you rate your pain IN THE PAST 7 DAYS when standing from a seated position."

The Subject responds verbally and the study coordinator or designee will record the response.

The NRS for Pain will be completed by the Subject and will take approximately 2 minutes to complete. The study coordinator or designee will enter the data into the eCRF.

# 10.12.3 Patient Reported Outcomes Measurement Information System (PROMIS)

PROMIS® instruments use modern measurement theory to assess patient–reported health status for physical, mental, and social well–being to reliably and validly measure patient–reported outcomes (PROs) for clinical research and practice. PROMIS instruments measure concepts such as pain, fatigue, physical function, depression, anxiety and social function. A copy of the PROMIS is located in Attachment 2.

The PROMIS questionnaire will take approximately 10 minutes to complete. After completion by the Subject the study coordinator, or designee, will enter into the eCRF.

#### 10.12.4 36-Item Short Form Health Survey (SF-36)

The SF-36 contains 36 questions assessing the Subject's health-related quality of life. A copy of the SF-36 is located in Attachment 3.

The SF-36 will take approximately 15 minutes to complete. After completion by the Subject, the study coordinator, or designee, will enter into the eCRF

#### 10.12.5 Subject Satisfaction Questions

Subject satisfaction questions will be verbally administered by the study coordinator or designee. Questions will take approximately 3 minutes to complete. The Subject satisfaction questions are located in Attachment 4.

#### 10.12.6 Self-reported Work Status Questions

The Self-reported Work Status Questions will be given to the subject for completion at Visit 1, Visit 4, Visit 5, Visit 6, and Visit 7. At Visit 1 / Screening, the questions are designed to assess the employment status of each subject prior to surgery. At each follow-up visit, the questions will reassess working status. Patients who return to work are asked whether they are doing the same type of work as prior to TKA. For applicable subjects, the self-reported date of Return to Work will be recorded. Subjects who have returned to work will also be asked if there are any limitations in the amount or type of work they are able to perform at their current job. Those subjects who have not returned to work will be asked the reason they have not returned to work.

The Self-reported Work Status Ouestions will take approximately 5 minutes to complete. The Work Status Questions are located in Attachments 5 and 6.

#### 11. STATISTICAL METHODOLOGY AND ANALYSES

#### 11.1 Introduction

This is a prospective, randomized, sham-controlled, multi-center, post-market trial to evaluate the iovera° device in treating pain associated with total knee arthroplasty (TKA). The study is designed to investigate whether iovera° treatment prior to TKA decreases cumulative patient opioid use over the course of 6 weeks following TKA while maintaining similar levels of pain relief.

The study will also investigate whether there is a relationship between patients treated with iovera° and length of hospital stay; patient reported pain and function as measured by WOMAC; patient satisfaction; and improved physical rehabilitation as measured by functional performance measures and range of motion.

The primary safety endpoint is the onset of device-related adverse events through twelve-weeks after TKA surgery. The primary measure of effectiveness is the Total Daily Morphine Equivalent (TME) of pain medications used from Day of Discharge to the 6-week follow-up visit. In addition. Change from Baseline in WOMAC Pain at the 6-week follow-up visit will be evaluated as a secondary endpoint. A variety of secondary effectiveness endpoints, including performance and pain assessments, will be measured.

Up to 8 study sites within the United States will screen a sufficient number of subjects to ensure that 150 subjects (Randomized 1:1 to approximate 75 Active Treatment subjects plus 75 Sham Treatment subjects) will be randomized and treated.

Subjects will be randomized either to receive therapeutic treatment with the iovera° treatment or to receive a sham treatment with the iovera° treatment, using a balanced 1:1 active-to-sham randomization stratified by Study Site.

